4.6.2. OLE Therapy Visit Windows

Table 4 defines the visit windows for assessments taken at 1-month intervals to be established with respect to relative day from the start of NEOD001 therapy in the OLE.

Table 4: OLE Therapy 1-Month Interval Visit Windows (Days)

Months	Target Study Day ^a	Analysis Window Study Day ^a	
		Low	High
OLE Baseline ^b	1	Closest visit to Day 1, prior to first OLE NEOD001 dose	
OLE Month 1	28	2	42 [= 28 + 28/2]
OLE Month 2	56	43 [= (28 + 28/2) + 1]	70 [= 56 + 28/2]
OLE Month x	28*x	$(x-1)*28 + 28/2 + 1$	$x*28 + 28/2$

OLE = open-label extension.

^a Study day will be calculated from first OLE dose date.

^b OLE Baseline is defined in Section 2.2.4.2.

Table 5 defines the visit windows for assessments taken at 3-month intervals to be established with respect to relative day from the start of NEOD001 therapy in the OLE.

Table 5: OLE Therapy 3-Month Interval Visit Windows (Days)

Months	Target Study Day ^a	Analysis Window Study Day ^a	
		Low	High
OLE Baseline ^b	1	Closest visit to Day 1, prior to first OLE NEOD001 dose	
OLE Month 3	84	2	126 [= 84 + 84/2]
OLE Month 6	168	127 [= (84 + 84/2) + 1]	210 [= (168 + 84/2)]
OLE Month x	28*x	$(x-3)*28 + 84/2 + 1$	$x*28 + 84/2$

OLE = open-label extension.

^a Study day will be calculated from first OLE dose date.

^b OLE Baseline is defined in Section 2.2.4.2.

Note that same scheme will be applied as described Section 4.6.1 when multiple records exist within the same analysis window.

5. ANALYSIS POPULATIONS

The NEOD001 Safety Population will include all subjects who received any amount of NEOD001 in the original parent study (NEOD001-001).

The OLE Safety Population will include all subjects who received any amount of NEOD001 in the OLE study.

The Cardiac Evaluable Population will include subjects who had cardiac involvement in the original parent study (NEOD001-001), defined as subjects who had an NT-proBNP \geq 650 ng/L at Screening and at least one post-baseline assessment of NT-proBNP.

The Renal Evaluable Population will include subjects who had renal involvement in the original parent study (NEOD001-001), defined as proteinuria $>0.5\text{g/day}$ in a 24-hour urine collection (the value reported as Total Protein on the Disease Specific Urine Laboratory Tests CRF) at Screening and at least one post-baseline assessment of proteinuria.

The Peripheral Neuropathy Evaluable Population will include subjects who had peripheral nerve involvement in the original parent study (NEOD001-001), defined as subjects who were marked as having had peripheral nerve involvement at baseline per the Amyloidosis Baseline Disease Assessment AND had a Screening peripheral neuropathy assessment score of 2 or greater from the Peripheral Neuropathy Assessment CRF and at least one post-baseline peripheral neuropathy assessment from the Peripheral Neuropathy Assessment CRF.

6. EXAMINATION OF SUBGROUPS

No prespecified evaluation of subgroups will be performed.

7. STUDY POPULATION

7.1. Subject Disposition

Subject disposition will be tabulated for all screened subjects and will include:

- the number of subjects dosed in the original parent study (NEOD001-001; NEOD001 Safety Population)
- the number of subjects screened in the OLE
- the number screened but not enrolled in the OLE
- the number enrolled in the OLE (OLE Safety Population)
- the number in each analysis organ evaluable population
- the number who discontinued treatment early in the OLE and reason(s) for discontinuation of treatment as recorded on the OLE eCRF
- the number who withdraw from OLE study prior to completing the study and reason(s) for withdrawal as recorded on the OLE eCRF

Time on study will be calculated as last known date of contact minus date of first infusion in NEOD001-OLE001 plus one.

By-subject data listings of all the above study disposition data including study completion and any reasons for premature treatment and/or study withdrawal will be presented.

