Peripheral Neuropathy Assessment ⁹	X	X	Every 3 months ¹⁰	X
SF-36 Health Survey ¹¹	X	X	Every 6 months ¹²	X
6MWT ¹³	X ¹⁴	X ¹⁴	Every 6 months ¹²	X
Echocardiogram		X	Every 12 months ¹⁵	X ¹⁶
ECG (12-lead in triplicate; local)	X	X	Every 3 months ^{10,17}	X
Vital Status Telephone Call				Every 3 months ¹⁸
Laboratory²¹				
Hematology & Chemistry ¹⁹	X	X	X	X
Amylase	X	X	X	X
Coagulation ²⁰	X	X	X	X
Troponin T	X	X	X	X
NT-proBNP ¹³	X	X	X	X
Pregnancy (WOCBP) ²²	X	X	X	X, X ²³
Serum Free Light Chain		X	Every 3 months ¹⁰	X
SPEP & 24-hour UPEP ²⁴		X	Every 3 months ^{10,25}	X
SIFE & UIFE		X	Every 3 months ^{10,25}	X
Urinalysis (dip stick) ²⁶		X	Every 3 months ¹⁰	X
24-hr Urine Protein Excretion ²⁴		X	Every 3 months ¹⁰	X
Other				
Serum NEOD001 Sample ²⁷	X	X	Every 3 months ¹⁰	X
Serum anti-NEOD001 Antibody Sample ²⁸	X	X	Every 3 months ¹⁰	X
NEOD001 Infusion ²⁹			X	

ECG = electrocardiogram; ECOG PS = Eastern Cooperative Oncology Group performance status; EOI = end of infusion; EOS = End of Study; INR = international normalized ratio; NT-proBNP = N-terminal pro B-type natriuretic peptide; NYHA = New York Heart Association; PK = pharmacokinetic; PT = prothrombin time; PTT = partial thromboplastin time; SF-36 = Short form-36; SIFE = serum immunofixation electrophoresis; 6MWT = 6-Minute Walk Test; SPEP = serum protein electrophoresis; UIFE = urine immunofixation electrophoresis; UPEP = urine protein electrophoresis; WOCBP = women of childbearing potential.

1. Rescreening is allowed once per subject. Only repeat tests that did not meet eligibility requirements.
2. Day 1 assessments may be conducted ±5 days from Day 1, with the exception of Month 1-Day 1 (i.e., no window is allowed at Month 1).

3. Conduct the EOS Visit 30 (± 5) days after last administration of study drug. Two additional evaluations are to be conducted beyond this time point, see Footnotes 18 and 23.
4. Obtain medical history since subject's last visit in Study NEOD001-001 (including all major hospitalizations and surgeries), as well as the subject's current medical status and prior therapies for AL amyloidosis. Adverse events that resolved prior to the subject's last visit in Study NEOD001-001 and prior to signing the ICF for this study should be assessed as possible medical history in this study.

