3.5 ESTIMATED STUDY AND TREATMENT DURATION

A subject's study duration may be up to 38 months or until the study is terminated (per Section 4.5), whichever occurs first. The study consists of a Screening Phase (1 month), Treatment Phase (36 months), and the End of Study (EOS) Visit 30 (\pm 5) days after the last dose.

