6.1.5 Vital Status Telephone Call

Conduct a vital status telephone call approximately 3 months after the subject's last study visit and approximately every 3 months thereafter for up to 5 years, death, or subject withdraws consent, whichever occurs first.

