The reporting period for AEs is from the time that the ICF is signed through 30 days after the last dose of study drug or last study visit, whichever is later. All AEs, whether or not related to the study drug, must be fully and completely documented in the eCRF and in the subject's medical notes. The following attributes must be assigned: description, dates of onset and resolution, severity, assessment of relatedness to study drug (either related or not related), and action taken. The Investigator may be asked to provide additional follow-up information.

In the event that a subject is withdrawn from the study because of an AE, it must be recorded in the eCRF. The subject should be followed and treated by the Investigator until the AE has resolved, stabilized, or a new chronic baseline has been established.

The Investigator must report all AEs. At each visit the Investigator will ask the subject a nonspecific question (e.g., "Have you noticed anything different since your last visit?") to assess whether any AEs have been experienced since the last report or visit. AEs will be identified and documented in the eCRF in appropriate medical terminology. The severity and the relationship to the study drug will be determined and reported in the eCRF (see Sections 7.2 and 7.3).

Note that any intermittent or as-needed ("PRN") use of medication (and specifically any newly prescribed medication) during the course of a study may indicate the occurrence of an AE that may need to be recorded on multiple eCRFs (e.g., AE and Concomitant Medication eCRFs).

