4.3. Partial Dates and Unknown Times

If only a partial date is available and is required for calculation, the following standards will be applied:

- Death Date
 - The last date that each subject was known to be alive will be identified as the greatest date associated with the subject’s completed assessments, including telephone contacts at which the subject was confirmed to be alive.
 - For missing day only – Day will be imputed as the first day of the month (i.e., 1) with the following exception: if the partial date falls in the same month as the last known alive date, then the partial date will be imputed to equal the last known alive date.
 - For missing day and month – Day and month will be imputed as the first day of the year (i.e., 1 January) with the following exception: if the partial date falls in the same year as the last known alive date, then the partial date will be imputed to equal the last known alive date.
- Start Dates (e.g., event date, AE onset date, start date of medication, or hospitalization admission date)
 - For missing start day only – Day will be imputed as the first day of the month (i.e., 1) with the following exception: if the partial date falls in the same month and year as the date being used in the calculation (e.g., first infusion date, informed consent date), then the partial date will be imputed to equal the date being used for the calculation.
 - For missing start day and month – Day and month will be imputed as the first day of the year (i.e., 1 January) with the following exception: if the partial date falls in the same year as the date being used in the calculation (e.g., first infusion date, informed consent date), then the partial date will be imputed to equal the date being used for the calculation.
 - When applicable, imputed start dates must be prior to the stop date.
- Stop Dates (e.g., AE resolution date or stop date of medication)
 - For missing stop day only – Day will be imputed as the last day of the month (i.e., 28, 29, 30, or 31).
 - For missing stop day and month – Day and month will be imputed as the last day of the year (i.e., 31 December).
 - Imputed stop dates must be on or after the start date.

If a time required for calculation related to exposure is missing, the following standards will be applied:

- If start time is missing for an infusion where the volume recorded on the eCRF is greater than 0 mL then start time will be imputed as the pre-dose time of vital signs at the same

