9.2.1.2. Cumulative Incidence Rates

The cumulative incidence rate is the probability that a particular AE occurs by a specified time. To compute the cumulative rate using the life table method, exposure time intervals from the first NEOD001 dose of the original parent study (NEOD001-001) (i.e., ≤1 month, >1 month to ≤3 months, >3 month to ≤6 months, >6 months to ≤1 year, >1 to ≤1.5 years, >1.5 to ≤2 years, >2 to ≤3 years, ..., and > maximum years) are specified, and the number of subjects at risk of experiencing an AE in each time interval is determined by taking the average number of subjects at risk at the start and end of each time interval. As subjects leave the study over time, the number of subjects at risk of experiencing the AE in each time interval decreases. The cumulative incidence rate over each time intervals is as follows:

$$1 - \{[1 - P(t_1)][1 - P(t_2)] \dots [1 - P(t_k)]\}$$

where $P(t_i)$ is the number of subjects with the AE divided by the number of subjects at risk in time interval t_i and where i ranges from 1 to k .

To illustrate the difference between crude and cumulative incidence rates and how these are computed, an example is provided (O'Neill, 1988). Suppose that 3000 subjects are initially exposed to a drug and followed for up to 1 year with varying durations of exposure (see Table 7). Assume further that 30 subjects experience SAEs, most of which occur later in the study as duration of exposure increases. The crude rate is $30/3000 = 0.01$ and the 12-month cumulative rate is 0.055. When AEs occur later in time as fewer subjects are at risk due to discontinuations or tolerability, the crude rate underestimates the longer-term risk and overestimates the shorter-term risk.

Using the example in Table 7, the number of subjects at the start of a time interval is the number of subjects at the start of the previous time interval minus the number of subjects lost to follow-up or who dropped out minus the number of subjects with SAEs. For instance, the number of subjects at the start of the 3rd time interval is equal to

$$[1800 - 399 - 1] = 1400$$

The proportion of subjects with SAEs at each time interval $P(t_i)$ is computed by dividing the number of subjects with SAEs by the number of subjects at risk in the time interval. For example, the number of subjects at risk for the 2nd time interval is as follows:

$$\frac{[1800 + (1800 - 399)]}{2} = 1600.5$$

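### The cumulative AE life table keeps subjects at risk through the parent-to-extension gap, when their events are not collected as AEs

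*SAP*

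**What the plan says.** **Life table.** SAP 9.2.1.2 measures time from the first NEOD001 dose in the parent study. It is applied to the OLE Safety Population and uses TEAEs from the start of the parent study. On leaving the risk set it says: "As subjects leave the study over time, the number of subjects at risk of experiencing the AE in each time interval decreases". It gives no censoring date and does not mention the interval between the two studies. SAP 9.2.3 to 9.2.9 use these cumulative rates for TEAEs overall and by severity, relatedness, dosing change, seriousness and death, withdrawal and infusion association.

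**AE collection.** Protocol 7.1: "The reporting period for AEs is from the time that the ICF is signed through 30 days after the last dose of study drug", or to the last study visit if later. The TEAE window in SAP 9.2 has the same end. Protocol Table 1 (footnote 4) has sites take a medical history covering the time since the last parent visit, "including all major hospitalizations and surgeries". Footnote 6 has them record AEs that were ongoing from that visit and at Screening.

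**Gap.** Protocol Table 1 has a screening column for subjects whose last parent visit was 60 days or more before, with no upper limit. SAP 2.2.4.1 resets the NEOD001 Baseline when more than 60 days separate the last parent dose from the first OLE dose. SAP 4.6.1 ties that limit to drug elimination.

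**Time on study.** SAP 7.1: "Time on study will be calculated as last known date of contact minus date of first infusion in NEOD001-OLE001 plus one". Protocol 3.5 says a subject's "study duration may be up to 38 months". Vital-status calls (Protocol 6.1.5) begin about 3 months after the last study visit and continue "approximately every 3 months thereafter for up to 5 years, death, or subject withdraws consent, whichever occurs first".

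**The concern.** A life table is valid only if everyone counted at risk in an interval could have had an event recorded in it. Between the end of parent AE reporting and OLE consent that fails. An event that begins and resolves there becomes medical history and does not enter the numerator, yet nothing takes the subject out of the denominator. Cumulative incidence after that point is then too low. Long-term safety is the primary objective, and these rates are the SAP's tool for describing risk that emerges late.

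A second, smaller matter concerns description. Time on study as defined may include years in which only survival is ascertained, and the SAP sets no AE-observed follow-up beside it. A reader could take the longer figure for safety follow-up.

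**Working it through.** **1. The SAP's own example.** Table 7 takes the number at risk as the average of those entering and those entering minus those lost, and cumulative incidence as 1 − Π(1 − events / at risk). In the second interval, (1800 + 1401)/2 = 1600.5 and 1/1600.5 = 0.0006. All 12 rows reproduce, ending at 0.05499 against the stated 0.055. The method is sound; what is missing is the rule for who is at risk.

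**2. Where the gap falls.** Inclusion criterion 1 requires at least 9 months of parent treatment. The gap therefore first affects the interval from 6 months to 1 year and everything cumulated after it. Earlier intervals are unaffected.

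**3. Size of the gap effect.** Assume a constant hazard λ, horizon T = 3 years, an uncollected gap g in every subject and no other censoring. Full capture gives 1 − exp(−λT). With the gap left in the risk set, the table gives 1 − exp(−λ(T − g)).

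| Uncollected gap | λ = 0.1/year | λ = 0.3/year |
|---|---|---|
| none | 0.259 | 0.593 |
| 30 days | 0.253 | 0.583 |
| 60 days | 0.247 | 0.573 |
| 180 days | 0.222 | 0.529 |
| 365 days | 0.181 | 0.451 |

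For 60 days the shortfall is 0.259 − 0.247 = 0.012 and 0.593 − 0.573 = 0.020. For 365 days it is 0.078 and 0.142. If only a share of subjects has such a gap, the shortfall shrinks in proportion to that share.

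Here g is time without AE collection, not time between doses. If parent AE reporting also ran 30 days past the last dose (an assumption) and consent came 28 days before the first OLE dose, a 60-day dose gap would leave 60 − 30 − 28 = 2 uncollected days. If parent reporting stopped at the last parent visit, a subject in the 60-days-or-more screening column would have about 60 days or more.

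**4. Time on study against AE-observed follow-up.** With k doses 28 days apart and EOS 30 days after the last, AE-observed time is 28(k − 1) + 30 + 1 days. Five years of calls add 1826 days; a single call at 3 months adds 91.

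| Doses | AE-observed (days) | With 5 years of calls | Ratio | Ratio, first call only |
|---|---|---|---|---|
| 36 | 1011 | 2837 | 2.8 | 1.09 |
| 12 | 339 | 2165 | 6.4 | 1.27 |
| 6 | 171 | 1997 | 11.7 | 1.53 |

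**The case against.** The tempting stronger reading is that the telephone calls dilute AE risk. The documents do not support it. Time on study appears only under disposition and starts at the first OLE infusion, whereas the life table starts at the first parent dose. Crude rates divide by subjects exposed (SAP 9.2.1.1), and no person-time rate is planned. The life table speaks of exposure intervals, TEAEs stop 30 days after the last dose or at the last study visit, and Protocol 4.4 ends participation at the EOS Visit. All of this points to an exit well before the last call. That part of the objection stands.

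The exit date is nevertheless unwritten. Protocol 4.4 adds that a subject whose vital status is known is not lost to follow-up, while Table 7 subtracts those lost. If everyone lost in Table 7 stayed at risk without AE capture, 0.055 would become 30/3000 = 0.010. That is a reason to state the date; it does not predict what the plan would produce.

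Three further points also stand:

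- The wording "including telephone contacts at which the subject was confirmed to be alive" belongs to the last-known-alive date used to impute death dates. That calls count as contact in SAP 7.1 is an inference; nothing excludes them.
- Capture outside the AE window is not nil. AEs ongoing from the last parent visit and at Screening are recorded, and late SAEs judged possibly related are reported (Protocol 7.4.4).
- Five years of calls after a full course is a ceiling, and an unlikely one, since SAP 11 records that the program was discontinued.

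None of this removes the gap. Even if the table were tied to duration of exposure in SAP 9.1, that duration runs from the first parent infusion to the last dose with delays included, so it spans the gap as well.

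**Conclusion.** The life-table point holds. As written, SAP 9.2.1.2 keeps subjects at risk between the end of parent AE reporting and OLE consent, and cumulative incidence after re-entry is biased low. At 3 years the bias is about 1 to 2 percentage points if every subject has a 60-day uncollected gap, and about 8 to 14 points for 365 days, under constant hazards of 0.1 to 0.3 per year. Hazards and gaps are assumptions. The gap distribution and the parent study's AE reporting window are not in the documents, so the actual effect could be small.

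The time-on-study point holds only as one of description. If calls count as contact, the figure can exceed AE-observed follow-up, at most 2837 against 1011 days after 36 doses. A reader might infer that this lowers an AE rate, but no planned rate uses it.

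**What to change.** In SAP 9.2.1.2, state that a subject is at risk from the first parent dose to the end of parent AE reporting, and again from OLE entry to the later of last dose plus 30 days and last study visit, with no time at risk in between. Say whether OLE entry means consent or first infusion, and count events from the same date. Because a subject may leave and re-enter within one wide interval, weight each subject by the fraction of the interval under AE collection, or use a product-limit estimate with start and stop times.

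In SAP 7.1, say whether vital-status calls count as contact. Report AE-observed follow-up (first OLE infusion to the later of last dose plus 30 days and last study visit) separately from vital-status follow-up.

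The cost is SAP wording and a little programming with study dates, including the end of parent AE reporting. Stated follow-up becomes shorter.

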7.2. Demographics and Baseline Characteristics

Demographic and baseline characteristics from as reported on the OLE Demographics eCRF will be summarized for the OLE Safety Population.

Demographic variables will include the following:

- Age at informed consent including the subgroups <65 vs \geq 65 years and <75 vs \geq 75 years
- Sex
- Race
- Ethnicity

Other baseline characteristics will include the following:

- Weight (kg)
- Height (cm)
- BMI (kg/m^2) including frequency of the following subgroups: <20, \geq 20 to <30, \geq 30 kg/m^2

Both conventional BMI and modified BMI (mBMI [$\text{kg}/\text{m}^2 \times \text{g}/\text{L}$], defined as subject's weight (kg)/subjects squared height (meters) \times serum albumin (g/L)) will be presented.

No inferential statistical comparisons will be performed.

All demographic and baseline characteristics data will be presented in by-subject data listings.

7.3. Baseline AL Amyloidosis Disease Characteristics

The following disease histories from the original parent study (NEOD001-001) will be summarized for the OLE Safety Population:

- Age (years) at AL amyloidosis diagnosis
- Duration (months) since AL amyloidosis diagnosis
- Number of derived involved organs (1, 2, 3, or 4 organs: cardiac, renal, peripheral neuropathy, and hepatic) based on the organ evaluable populations defined in Section 5
- Number of physician assessed involved organs (gastrointestinal, autonomic nervous system, lung, soft tissue/lymphatic, or other) as recorded on the eCRF
- Total number of involved organs (derived plus physician assessed; range 1-9)
- Screening NT-proBNP: <1800 ng/L, ≥1800 ng/L
- NYHA Class: I, II, III, IV
- Baseline FLC Ratio: Low (<0.26), Normal (0.26 – 1.65), High (>1.65)

In addition, from the OLE Baseline 6MWT distance (meters) will be summarized including frequency of the subgroups: <300 meters vs. ≥300 meters.

No inferential statistical comparisons will be performed.

Baseline disease characteristics will be presented in by-subject data listings.

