2.3.3.4. Cardiac Endpoints

The following endpoints will be evaluated in the Cardiac Evaluable Population (see Section 5).

For these subjects, cardiac response, as assessed by N-terminal pro-brain natriuretic peptide (NT-proBNP), categories are defined as (modified from Table 2 in [Comenzo, 2012](#)):

Response	Stable Disease	Progression
Decrease in NT-proBNP from baseline of >30% and >300 ng/L or decrease in NYHA class of ≥ 2 in subjects with baseline NYHA class III or IV	Assessment was neither Response nor Progression	Increase in NT-proBNP from baseline of >30% and >300 ng/L

Best response is defined as the most favorable category (response, stable, or progression) across all visits. Subjects will be classified as responders or non-responders. Non-response is defined as either stable or progression.

- Cardiac response from NEOD001 and OLE baselines (see Section 2.2.4), as assessed by NT-proBNP response criteria, at each visit
- Cardiac best response from NEOD001 and OLE baselines (see Section 2.2.4), as assessed by NT-proBNP response criteria. Best response will be over the course of the study.
- Change and percent change from NEOD001 and OLE baselines (see Section 2.2.4) to each visit in NT-proBNP

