2.3.3.5. Renal Endpoints

The following endpoints will be evaluated in the Renal Evaluable Population (see Section 5).

For these subjects, renal response categories (modified from [Palladini, 2014](#)) are defined as:

Response	Stable	Progression
$\geq 30\%$ decrease from baseline or $< 0.5\text{g}/24$ hours post-baseline result of proteinuria (measured by 24-hour urine total protein excretion) in the absence of renal progression	Assessment was neither Response nor Progression	$\geq 25\%$ decrease in eGFR from baseline Note: if assessment qualifies as both Response and Progression, then assessments will be counted as progression

Best response is defined as the most favorable category (response, stable, or progression) across all visits. Subjects will be classified as responders or non-responders. Non-response is defined as either stable or progression.

- Renal response from NEOD001 and OLE baselines (see Section 2.2.4) at each visit
- Renal best response from NEOD001 and OLE baselines (see Section 2.2.4). Best response will be evaluated over the course of the study.
- Change and percent change from NEOD001 and OLE baselines (see Section 2.2.4) to each visit in creatinine, proteinuria, and estimated glomerular filtration rate (eGFR)
- Time to eGFR ≤ 15 mL/min/1.73 m² (Chronic Kidney Stage 5) from NEOD001 and OLE baselines (see Section 2.2.4)

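### SAP 7.3 counts liver among organs derived from Section 5, which has no hepatic population, and SAP 2.3.3.5 can list a subject with unchanged or rising proteinuria as a renal responder

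*SAP*

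**What the plan says.** **Organ count.** SAP 7.3 summarizes parent-study disease history for the OLE Safety Population. Its derived count has categories 1, 2, 3 or 4, for "cardiac, renal, peripheral neuropathy, and hepatic) based on the organ evaluable populations defined in Section 5". A second line covers organs judged by the physician: "Number of physician assessed involved organs (gastrointestinal, autonomic nervous system, lung, soft tissue/lymphatic, or other) as recorded on the eCRF". A third adds the two: "Total number of involved organs (derived plus physician assessed; range 1-9".

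SAP 5 defines three organ populations:
- **Cardiac:** "The Cardiac Evaluable Population will include subjects who had cardiac involvement in the original parent study (NEOD001-001", with Screening NT-proBNP of at least 650 ng/L.
- **Renal:** "The Renal Evaluable Population will include subjects who had renal involvement in the original parent study (NEOD001-001), defined as proteinuria" above 0.5 g/day.
- **Peripheral neuropathy:** involvement marked at baseline and a Screening score of at least 2.

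Each also needs later data; for renal the words are "at Screening and at least one post-baseline assessment of proteinuria". There is no hepatic population. SAP 2.1.3 names hepatic response as an objective, but SAP 2.3.3 has no hepatic endpoint.

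**Renal response.** SAP 2.3.3.5 works in the Renal Evaluable Population and lists "Renal response from NEOD001 and OLE baselines (see Section 2.2.4) at each visit". Response is a fall in proteinuria of at least 30%, or any post-baseline value below 0.5 g/24 h, provided there is no progression (an eGFR fall of at least 25%). Under SAP 2.2.4.2 the OLE baseline for proteinuria is the most recent value before the first OLE infusion, with no minimum. Under SAP 2.2.4.1 the NEOD001 baseline is also that pre-OLE value when more than 60 days separate the last parent dose from the first OLE dose.

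**The concern.** A programmer told to build a four-organ count from Section 5 finds three sources. The table will then either understate disease extent in subjects with liver involvement or be completed by an unwritten rule. Because efficacy has been cut back to listings, the SAP 7.3 table is one of the summaries that will actually be produced.

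The renal problem is a mismatch of time points. Membership of the renal population guarantees proteinuria above 0.5 g/day at parent Screening, so from a baseline near that time a later value below 0.5 g/24 h is a real fall. OLE baseline comes after at least 9 months of parent-study treatment, and nothing guarantees that proteinuria is still above 0.5 g/24 h. For a subject already below it, the criterion is met without any change. That label also feeds best response (SAP 2.3.3.5), and time to first organ response from the first OLE infusion and duration of response (SAP 2.3.3.1).

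**Working it through.** **1. Organ count**

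Inputs: 4 organs named in the derived count (SAP 7.3); 5 physician-assessed categories (SAP 7.3); 3 organ populations (SAP 5).

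- Plan's own figure, from the organs named: 4 + 5 = 9. This reproduces the stated upper limit.
- Same sum from the source that SAP 7.3 prescribes: 3 + 5 = 8, with a derived maximum of 3. This does not match the stated 9 and 4.

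The stated range is reached only if liver is counted, and the prescribed source cannot count it.

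Which subjects are affected: four organs give 2^4 − 1 = 15 non-empty combinations. Liver is in 2^3 = 8 of them, and each of those 8 is one short. The liver-only combination gives a derived count of 0, for which the table has no category.

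**2. Renal rule**

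With B the proteinuria at the baseline in use and P the post-baseline value (g/24 h):
- Progression if eGFR has fallen by ≥25%;
- otherwise Response if (B − P)/B ≥ 0.30 or P < 0.5;
- otherwise Stable.

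The values below are illustrative assumptions; the documents give no subject data.

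| B | P | Change in proteinuria | eGFR fall | Category |
|---|---|---|---|---|
| 0.20 | 0.45 | (0.45 − 0.20)/0.20 = +125% | 0% | Response |
| 0.10 | 0.49 | +390% | 0% | Response |
| 0.30 | 0.30 | 0% | 0% | Response |
| 0.20 | 0.40 | +100% | 24% | Response |
| 0.20 | 0.40 | +100% | 25% | Progression |
| 0.40 | 0.50 | +25% | 0% | Stable |
| 0.60 | 0.49 | −18.3% | 0% | Response |

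The last row is a genuine crossing of the threshold. The first four are not falls at all.

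Over a grid of B and P up to 3.00 in steps of 0.01 g/24 h, with stable eGFR, every rise scored as Response had B of 0.48 or less. That is expected: P must be 0.49 or less, and B must be lower still.

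**3. After the fix**

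If P < 0.5 counts only when B > 0.5, both routes to Response require P < B. No unchanged or rising value can then be a Response. If hepatic involvement is defined, the maxima return to 4 and 9.

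**The case against.** The best reply is that little depends on either point. Liver may have been recorded under *other* on the eCRF, which would restore the subject's total. Efficacy endpoints go to by-subject listings without tables or figures (SAP 8 and 11), so no response rate or time-to-response summary can be distorted, and a reader of the listing can see the proteinuria values. Most of this stands and limits the size of the problem. It does not restore the derived count, supply the missing category, or make the renal label correct.

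A reader might infer more than the documents support:

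- *Taking involvement from parent Screening lowers the counts.* It does not. SAP 7.3 says it reports parent-study history, so that is the right time point.
- *Liver disappears from both counts.* This is not established, because of *other*; the eCRF is not among the documents.
- *The post-baseline condition removes many involved subjects.* This is unlikely for heart and kidney. Every OLE subject had at least 9 months of parent treatment, and the OLE schedules NT-proBNP monthly and 24-hour urine protein every 3 months. The condition is out of place in a baseline characteristic, but no undercount from it is shown.
- *The neuropathy score of at least 2 is an error.* It is a stated threshold, like 650 ng/L and 0.5 g/day.
- *The cardiac rule is faulty in the same way.* It requires "Decrease in NT-proBNP from baseline of >30% and >300 ng/L", which cannot be met from an OLE baseline of 300 ng/L or less. But this is a stated, conservative criterion that creates no false responder, and the same rule has an NYHA route for subjects in class III or IV at baseline.

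**Conclusion.** Both points hold as defects in stated rules.

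The derived organ count cannot be produced as SAP 7.3 describes it: its maximum is 3 rather than 4, and the total's is 8 rather than 9. A subject with liver involvement is one short in the derived count, and in the total unless liver was entered under *other*. A subject in none of the three populations cannot be placed. This reaches a summary table.

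The renal rule labels as Response any post-baseline value below 0.5 g/24 h without eGFR progression, even when proteinuria has not changed or has risen. This requires a baseline in use below 0.5 g/24 h: either the OLE baseline, or a NEOD001 baseline reset to the pre-OLE value after a gap of more than 60 days. It affects listings only.

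Neither the number of subjects with liver involvement nor the number below 0.5 g/24 h at OLE baseline is given. So it is not known whether any subject is in fact misclassified, and it would be wrong to say that reported response rates are inflated, since none is planned.

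**What to change.** **SAP 5 and 7.3.** Define hepatic involvement from parent-study baseline data, if it was collected. SAP 5 cites the baseline disease assessment form only for peripheral nerve, so the availability of liver data must be confirmed first. If it was not collected, delete hepatic and correct the ranges to 0-3 derived and a maximum total of 8. Either way, base the count on the involvement criteria at parent Screening or baseline without the post-baseline condition, keep that condition for the evaluable populations, and add a 0 category. If hepatic is derived, state that liver entered under *other* is not counted twice.

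**SAP 2.3.3.5.** Let a value below 0.5 g/24 h count as Response only when proteinuria at the baseline in use was above 0.5 g/24 h. Flag other subjects as not evaluable on that criterion; the 30% fall stays open to them. Wording the condition on the baseline in use covers the reset NEOD001 baseline as well.

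**Cost.** Wording and derivation changes, with no new data collection. Fewer subjects will be evaluable on the 0.5 g criterion, and that change is visible in listings only.
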